## 1.4 Summary of known potential benefits and risks

### 1.4.1 Benefits

Selexipag, a non-prostanoid IP (prostacyclin) receptor agonist, is an orally available medicine with PK characteristics suitable for b.i.d. dosing.

The efficacy of selexipag in the treatment of adult patients with symptomatic PAH was demonstrated in GRIPHON, the largest (N = 1,156) and only long-term (mean duration 1.5 years and up to 4.2 years), controlled outcome study conducted with an IP-receptor agonist. The treatment effect was consistent across WHO FC II-III and was fully preserved in patients already treated with an approved PAH-specific medicine at baseline (80% of the study population), as well as in patients treated with two such medicines (30% of the study population).

GRIPHON was the first study to demonstrate the outcome benefit of an IP-receptor agonist, in particular when added sequentially to therapies acting on other pathogenic pathways in PAH (endothelin and nitric oxide pathways), i.e., within a treatment strategy consistent with current consensus guidelines whereby selexipag is the only IP-receptor agonist given a Class I evidence recommendation for sequential drug combination therapy [[Galiè 2015](#)].

Pediatric PAH is a rare and progressive disorder associated with considerable morbidity and mortality. Current treatment recommendations in the pediatric population include PDE-5 inhibitors, ERAs, and inhaled, subcutaneous, and i.v. prostacyclin-pathway agonists [[Ivy 2013](#), [Galiè 2015](#)]. However, in the absence of randomized controlled clinical trials powered to show the efficacy of those therapies in pediatric patients, the treatment algorithm is based on evidence from adult studies.

Further clinical trials in the pediatric population are therefore extremely important to provide more data for the management of PAH in children.

Given the pathophysiological and clinical similarities of pediatric and adult PAH disease, it is believed that pediatric participants with PAH could benefit from selexipag treatment. This study aims to determine the appropriate dose and to investigate the PK, safety, and tolerability of selexipag in pediatric participants over 2 years of age with PAH.

### 1.4.2 Risks

The tolerability and safety profile of selexipag administered to children is expected to be consistent with that of adult patients [see Section [1.2.3.4](#)].

The following measures are being taken to minimize the potential risks for the pediatric participants participating in the study:

- The selection of the starting dose for pediatric participants is based on their body weight category, using the data from the population PK model in the GRIPHON study, targeting the exposure observed in adult participants with PAH at a starting dose of 200 µg.
- At the interim and final PK analyses, all available PK results will be used to update the PK model and to confirm or adjust the dose selection.
- Enrollment of Cohort 3 (children aged from 2 to less than 6 years old) will only be performed after the PK interim analysis in Cohorts 1 and 2 (pediatric participants older than 6 years) have been completed, and selexipag safety and tolerability profiles in Cohorts 1 and 2 have been confirmed.
- The number of PK samples and blood volume collected per participant will be optimized to reduce the total amount of blood drawn from pediatric participants [see Section 7.2.5.1].
- Inclusion and exclusion criteria are carefully designed in this protocol [see Section 4].
- Close monitoring during the initial up-titration period up to Week 12 includes weekly phone calls or site visits, followed by 3-monthly contacts (phone calls and site visits alternating every 3 months) [see Figure 2, Table 4, and Table 5].
- Specific recommendations are made regarding the management of AEs associated with tolerability during the initial up-titration phase [see Section 5.1.4], along with the recommendation that participants take study drug with food to improve tolerability [see Section 5.1.4].
- Specific recommendations are made for study drug interruption and/or permanent discontinuation [see Section 5.1.10].
- Guidance to investigator and parents/participants in case of clinical signs compatible with gastrointestinal ileus or obstruction [see Sections 1.2.2 and 5.1.10].
- Guidance to investigator and parents/participants in case of clinical signs of hyperthyroidism [see Sections 1.2.3.4 and 5.1.10].
- Monitoring of participants' growth and development throughout their study participation [see Sections 7.2.3.4. and 7.2.3.5].

Safety surveillance for participants participating in study AC-065A203 will additionally be ensured by an Independent Data Safety Monitoring Committee (IDMC), which will periodically review available safety data [see Section 3.3].

Participants will receive additional care as result of being in a clinical trial including close monitoring at an expert PAH center.

It is the investigator's responsibility to monitor the benefit-risk ratio of study treatment administration, as well as the degree of distress caused by study procedures on an individual participant level, and to discontinue study treatment or study procedures if, on balance, they determine that continuation would be detrimental to the participants' well-being.

### 1.4.3 Conclusion

The benefit of medicines acting on the prostacyclin pathway (IP-receptor agonists) in the treatment of PAH in adults is established, as acknowledged by current treatment guidelines [[Galiè 2015](#)].

Uptravi (selexipag) is a selective IP-receptor agonist for oral use with proven efficacy and safety in adults with PAH. To date, selexipag is the only IP-receptor agonist approved globally for long-term treatment across WHO FC II III, and primarily in combination with current first-line oral PAH-specific medicines, in adult patients in need of additional therapy because of insufficient disease control. Uptravi represents an important additional treatment option for these patients.

Selexipag is not indicated or foreseen for use as an alternative to i.v. prostacyclin analogs (epoprostenol, treprostinil) in patients with the most severe PAH (WHO FC IV).

The availability of selexipag, a highly selective IP-receptor agonist for oral use and with demonstrated benefit for PAH disease outcomes in add-on therapy, provides an important rationale for initiating prostacyclin-pathway therapy at a medically appropriate stage of PAH disease without major consequences for the patient's lifestyle.

Based on the known similarities between PAH disease in adult and pediatric patients and the need to develop treatments that may be disease-modifying in pediatric patients with PAH, this study is the first clinical study conducted with selexipag in children with PAH.

## 2 STUDY OBJECTIVES

### 2.1 Primary objective(s)

The primary objective of the study is to confirm the selexipag starting dose(s), selected based on PK extrapolation from adults, that leads to similar exposure as adults doses in children from  $\geq 2$  to  $< 18$  years of age with PAH, by investigating the PK of selexipag and its active metabolite ACT-333679 in this population.

## 2.2 Secondary objectives

- To evaluate the safety and tolerability of selexipag in children from  $\geq 2$  to  $< 18$  years of age with PAH.

## 2.3 Exploratory objectives

- To explore the relationship between drug exposure at the iMTD and 6MWD at each time point of assessment.
- To explore the relationship between drug exposure and NT pro-BNP at each time point of assessment.
- To explore the relationship between drug exposure and Echo variables at each time point of assessment.
- To explore the time to disease progression / clinical worsening from first study drug dose up to EOT + 7 days.

## 2.4 Other objectives

- To assess the palatability of selexipag formulation at each time point of assessment using a 5-point facial hedonic scale.
- To assess the acceptability of selexipag formulation at each time point of assessment using a 3-point categorical scale.

## 3 OVERALL STUDY DESIGN AND PLAN

### 3.1 Study design

This is a prospective, multi-center, open-label, single-arm Phase 2 study.

Approximately 60 participants will be enrolled in 3 different age cohorts (based on age at Baseline / Enrollment / Visit 2) to obtain at least 45 participants with evaluable PK profiles:

- Cohort 1:  $\geq 12$  to  $< 18$  years of age (approximately 20 enrolled participants to obtain at least 15 participants with evaluable PK profiles)
- Cohort 2:  $\geq 6$  to  $< 12$  years of age (approximately 20 enrolled participants to obtain at least 15 participants with evaluable PK profiles)
- Cohort 3:  $\geq 2$  to  $< 6$  years of age (approximately 20 enrolled participants to obtain at least 15 participants with evaluable PK profiles).

The starting dose is based on the body weight category of the participants, using the data from the population PK model in the GRIPHON/AC-065A302 study targeting the exposure observed in adult participants with PAH at a starting dose of 200 µg [[Modeling and Simulation Report AC-065A302 \(GRIPHON\) 2014](#)]. The continuous relationship between dose and body weight is used to define body weight categories and starting dose for each body weight category such that on average the exposure (combined exposure over one dosing interval at steady state [ $AUC_{\tau,ss,combined}$ ]) will be comparable to that in a 70 kg adult but not exceeding the exposure in a 50 kg adult [[Figure 1, Modeling and Simulation Report, Pediatric dose selection 2016](#)]:

[figure not shown]
- 100 µg for participants with a body weight from  $\geq 9$  to  $< 25$  kg.
- 150 µg for participants with a body weight from  $\geq 25$  to  $< 50$  kg.
- 200 µg for participants with a body weight  $\geq 50$  kg.

The body weight-exposure relationship is extrapolated from the body weight-exposure relationship determined by the population PK model in participants with PAH in the GRIPHON study with body weights ranging from 40–148 kg. In this model, body weight was a covariate on selexipag and ACT-333679 volume of distribution and elimination rate [[Modeling and Simulation Report AC-065A302 \(GRIPHON\) 2014](#)].

Confidential

**Figure 1** Estimated starting doses based on the GRIPHON PK model achieving the same exposure as in adult patients of 50 kg, 70 kg, and 96 kg treated with 200 µg b.i.d. selexipag

AUC area under the curve; b.i.d. twice daily; GRIPHON prostacyclin (PG12) receptor agonist in pulmonary arterial hypertension; PK pharmacokinetic.

The exposure is defined as the combined exposure to selexipag and ACT-333679 corrected for potency ( $AUC_{\tau,ss,combined}$ ). It is derived accordingly:

$$AUC_{\tau,ss,combined} = 1/38 \times AUC_{\tau,ss, selexipag} + 37/38 \times AUC_{\tau,ss ACT 333679}$$

The potency of ACT-333679 was estimated to be 37 times that of selexipag. ACT-333679 is, therefore, the major contributor to the efficacy of selexipag [Menyhart 2014]. The starting dose selection will be confirmed or adjusted after the completion of each age cohort by updating the population PK model (interim analysis).

The study will be conducted in approximately 30 sites in 20 countries.

Enrollment will start with both Cohort 1 and Cohort 2 (participants  $\geq 12$  to  $< 18$  and  $\geq 6$  to  $< 12$  years old, respectively). After completion of PK assessments in at least 15 participants from Cohort 1 at Week 12, the dose-exposure relationship will be established using a population PK model [Modeling and Simulation Report, Pediatric dose selection 2016]. The PK data from any participants in Cohort 2 who have completed their PK assessments at this time will be included in this first interim analysis.

Results of this model-based analysis will be used to confirm or adjust the selexipag doses initially selected. If the population PK model results suggest that the administered selexipag doses lead to exposures deviating from the currently predicted target exposures, the recommended starting dose, increments of up-titration, and maximum allowed dose (equivalent to 1,600 µg b.i.d. in adult participants with PAH) for the remaining participants to be enrolled in Cohort 2 and Cohort 3 will be adjusted. The decision on dose-adjustment will take into account the inter-individual variability in the pediatric population and the difference in exposure between lower and upper limits of body weight in the GRIPHON study. The inter-individual variability in the GRIPHON study was more than 30% (comparing the 10th and 90th percentiles), and difference in exposure between lower and upper limits of body weight was 50% [[Modeling and Simulation Report AC-065A302 \(GRIPHON\) 2014](#)]. It is expected that the dosing regimen does not need to be adjusted if the revised point estimate body weight-starting dose relationship deviates from the current estimate by less than 30%. The dosing regimen must be adjusted if the revised point estimate body weight-starting dose relationship deviates from the current estimate by more than 50%. If this difference between the revised and the current point estimate is between 30% and 50%, the decision on dose adjustment will depend on the results of safety assessments after the first dose. Enrollment of Cohort 3 (children  $\geq 2$  to  $< 6$  years of age) will start once the appropriate doses have been confirmed by modelling and simulation in a second interim analysis of PK data from the children older than 6 years (i.e., Cohorts 1 and 2), and if there is no safety concern based on IDMC reviews.

The PK data pooled from all three age cohorts will be modelled to allow dosing recommendations for all children  $\geq 2$  years of age. A final PK analysis will be prepared based on the overall PK and safety data up to Week 16 evaluation.

Given the rareness of pediatric PAH, combined with the ongoing global Corona virus disease-2019 (COVID-19) pandemic, enrolling participants in age Cohort 3 ( $\geq 2$  to  $< 6$  years of age) into this study has been difficult and as such the planned sample size of at least 15 PK evaluable Cohort 3 participants remains a challenge. The option of confirming the selexipag dosing recommendation for participants aged  $\geq 2$  to  $< 6$  years based on a smaller sample size is, therefore, being considered. To assess this, a third interim PK analysis may be conducted, as deemed appropriate by the sponsor.

All available PK and safety data from participants in Cohorts 1, 2, and 3 up to Week 16 at the time of the data cut-off date, will be included in interim analysis 3. The analytical approach for interim analysis 3 will be the same as applied for interim analyses 1 and 2. For the dosing confirmation of Cohort 3 with fewer than the planned 15 PK evaluable participants, one of the following criteria is to be achieved:

- The 90% CI of the point estimate describing the body weight-starting dose relationship relative to the current estimate is within 0.70-1.30.

*Or*

- The 90% CI of the point estimate describing the body weight-starting dose relationship relative to the current estimate is within 0.50-1.50 and at the same time, no dose adjustment is warranted by the available safety data.

If, however, the 90% CI of the relative point estimate exceeds 0.70-1.30 and a dose adjustment may be warranted by the available safety data or the 90% CI of the relative point estimate exceeds 0.50-1.50, a final PK analysis including the PK data pooled from all 3 age cohorts and at least 15 PK available participants in Cohort 3, will be conducted. Following this final PK analysis, the dosing recommendation will be confirmed based on the revised point estimate body weight-starting dose relationship, irrespective of the 90% CI, as originally planned.

In case the dosing recommendation for age Cohort 3 is confirmed based on the third interim PK analysis, further enrolment into the trial will be terminated. The PK of all enrolled participants, including participants completing their PK assessments after the data cut-off date for interim analysis 3 will be included in the PK analysis to be reported in the clinical study report (CSR).

The selection of the dosing regimen for the Phase 3 study will be based on the safety, tolerability, and PK results evaluated in the interim or final PK analysis (as applicable).

Participants who discontinue the treatment any time before the profile PK sampling day may be replaced within the age cohort.

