Based on the pediatric PK data available at the second interim analysis, the planned sample size for Cohort 3 (N 10) was assessed using a simulation/estimation approach. Pediatric datasets were simulated with fold-deviations of exposures ( $AUC_{\tau,ss,combined}$ ) of 0.5, 0.7, 1, 1.3, and 1.5-fold compared to the adult reference model [[PK Interim Analysis Report-2 AC-065A203 2020](#)]. Based on this analysis, the power of recognizing a pediatric to adult ratio of 0.5, 0.7, 1.3, and 1.5 as significantly different from 1, is predicted to be >99%, 82.8%, 56.4%, and 83.2%, respectively. Type 1 error (i.e., when the AUC ratio is 1) is estimated to be 11.8%. If the sample size of Cohort 3 is increased to 15, the estimated values of the power are predicted to be >99%, 91.6%, 71.2% and 96.2% for the exposure ratios of 0.5, 0.7, 1.3, and 1.5, respectively, and the Type 1 error is estimated to be 11.0% [[PK Interim Analysis Report-2 AC-065A203 2020](#)]. Based on this assessment, the planned sample size for Cohort 3 has been increased to at least 15 PK evaluable participants in order to ensure a power of at least 70% for all potential outcomes.

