#### 14.7.2.2.3.2 Final PK analysis

In the final analysis, model parameters were estimated using the pooled data from all age cohorts. Compared to the second interim analysis, the youngest age cohort ( $\geq 1$  to  $< 2$  years) was added to the analysis dataset and all parameters besides the non-identifiable ones were estimated.

Parameters could be estimated well when pooling data from all age cohorts. The median estimation errors were  $< 45\%$  for all parameters [Table 9]. For some simulated datasets, the estimation error for the IIV on  $K_m$  and the body weight effect on the clearance were high. The resulting  $AUC_{\tau,ss,combined}$  prediction uncertainty was on average below 1.4-fold for subjects of 17, 35 and 59 kg [Table 6]. Although the body weight effect on the clearance had high estimation error in some runs, the maximal prediction uncertainty was only 1.6.

Confidential

**Table 6 Prediction uncertainty of  $AUC_{\tau,ss,combined}$  based on simulated data for children  $\geq 1$  to  $< 18$  years of age (Cohorts 1, 2, and 3)**

Body weight (kg)	<math>AUC_{\tau,ss,combined}</math> prediction uncertainty (fold)			
	median	mean	min	max
17	1.38	1.39	1.23	1.60
35	1.23	1.23	1.14	1.34
59	1.34	1.34	1.19	1.61

$AUC_{\tau,ss,combined}$  Combined exposure over one dosing interval at steady state.

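### Does the interim 3 confidence-interval rule need a stated body weight or ratio before it can end enrolment?

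*Protocol*

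**What the plan says.** Section 3.1 of the protocol sets two alternative conditions that apply "For the dosing confirmation of Cohort 3 with fewer than the planned 15 PK evaluable participants". Criterion 1: "The 90% CI of the point estimate describing the body weight-starting dose relationship relative to the current estimate is within 0.70-1.30". Criterion 2 widens the limits to 0.50-1.50 and adds that the available safety data must not call for a dose adjustment. If dosing is confirmed, "further enrolment into the trial will be terminated". If neither criterion holds, a final analysis with at least 15 evaluable Cohort 3 children follows, and its recommendation rests on the point estimate, "irrespective of the 90% CI, as originally planned".

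The same section says of the starting doses that "The continuous relationship between dose and body weight is used to define body weight categories". It also says that interim 3 uses the analytical approach of interims 1 and 2. Section 10.5 sizes Cohort 3 from a simulation: "Pediatric datasets were simulated with fold-deviations of exposures", and it reports "the power of recognizing a pediatric to adult ratio of 0.5, 0.7, 1.3, and 1.5 as significantly different from 1". Appendix 7 (Section 14.7.2.2.3.2) reports precision by body weight: the "prediction uncertainty was on average below 1.4-fold for subjects of 17, 35 and 59 kg".

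Sections 10.2.1.1 and 10.4 send the modelling and interim details to a modelling data analysis plan. The Amendment 7 summary of changes gives, as its reason for editing Section 10.2.1.1, that this plan will be updated for the third interim. SAP Section 1 leaves PK modelling to separate plans. SAP Section 1.2 reports interims 1 and 2 as already done.

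**The concern.** The rule compares a curve with a curve. If the weight effects are re-estimated, the revised-to-current ratio can differ by weight, and so can the width of its interval. Section 3.1 names no weight, parameter or averaging rule. Two candidates appear elsewhere: one pediatric-to-adult exposure ratio (Section 10.5, at the same values 0.5, 0.7, 1.3 and 1.5) and the curve at 17, 35 or 59 kg (Appendix 7). They also sit on different scales, exposure and dose. It is not stated either whether the current estimate is the original adult-model curve or the one updated at interim 2.

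Interim 3 is the only analysis at which an interval decides. A pass stops recruitment with fewer than 15 evaluable children aged 2 to under 6 years. The study is open-label and the sponsor chooses whether to run the analysis. If the quantity were picked after the data were seen, the same data might pass on one reading and fail on another.

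**Working it through.** **Consistency of the plan's own figures.** Section 10.5 gives power but no standard error, so its figures cannot be recomputed directly. Assume a two-sided 10% test on the log ratio; the stated Type 1 errors are 11.8% (10 children) and 11.0% (15). Then SE = |ln r| / (1.645 + z_power).

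| Cohort 3 | r | Power | SE | Fold = exp(1.645 × SE) |
|---|---|---|---|---|
| 10 | 0.7 | 82.8% | 0.138 | 1.25 |
| 10 | 1.3 | 56.4% | 0.145 | 1.27 |
| 10 | 1.5 | 83.2% | 0.156 | 1.29 |
| 15 | 0.7 | 91.6% | 0.118 | 1.21 |
| 15 | 1.3 | 71.2% | 0.119 | 1.22 |
| 15 | 1.5 | 96.2% | 0.119 | 1.22 |

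At 15 children one SE (0.1185) returns 91.4%, 71.5% and 96.2%, in line with the plan. At 10 children no single SE fits: the mean, 0.146, returns 78.7%, 56.0% and 87.1%. The single-ratio precision at 10 is therefore approximate.

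**What the limits can hold.** Write fold for the upper 90% limit divided by the estimate, and assume a log-symmetric interval. The estimate must lie between lower limit × fold and upper limit / fold. This window is empty once fold exceeds √(1.30/0.70) = 1.363 for criterion 1, or √(1.50/0.50) = 1.732 for criterion 2.

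**Chance of meeting each set of limits** (true ratio 1, log-normal estimate, SE = ln(fold)/1.645, 10 Cohort 3 children; Appendix 7 Table 6 mean folds):

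| Reading | Fold | Criterion 1 window | Criterion 1 | Criterion 2 limits |
|---|---|---|---|---|
| Single ratio, Section 10.5 | 1.25-1.29 | 0.88-1.04 to 0.90-1.01 | 26-43% | 83-90% |
| Curve at 17 kg | 1.39 | 0.973 to 0.935, empty | 0% | 61% |
| Curve at 35 kg | 1.23 | 0.861-1.057 | 55% | 94% |
| Curve at 59 kg | 1.34 | 0.938-0.970 | 7% | 73% |

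Table 6 gives a range at 17 kg of 1.23 to 1.60, so criterion 1 there runs from 55% down to 0%, and the criterion 2 limits from 94% down to 19%.

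**Scale.** Under dose proportionality the dose ratio is the inverse of the exposure ratio. An exposure ratio of 0.93 with a 1.27-fold interval is 0.93/1.27 = 0.73 to 0.93 × 1.27 = 1.18, inside 0.70-1.30. As a dose ratio it is 1/0.93 = 1.08, with limits 1/1.18 = 0.85 and 1/0.73 = 1.37, outside.

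**What the contrast can bear.**

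- The single-ratio row comes from simulations informed by the pediatric data at interim 2. Table 6 predates any pediatric data, re-estimates all identifiable parameters, and leaves out the trough samples that the real analysis will use (Section 14.7.3). The gap between 26-43% and 0% therefore mixes data and model with reading.
- The 0% depends on 1.39 against 1.363, and 1.39/1.363 = 1.02. A 2% narrower interval opens the window.
- 35 and 59 kg lie outside the 10-24 kg that Appendix 7 assumes for Cohort 3, so those rows are not plausible choices for this rule.
- Criterion 1 fails more often than not on the single-ratio reading too. Failing it does not keep recruitment open. That requires either an interval beyond 0.70-1.30 together with a possible safety-driven adjustment, or an interval beyond 0.50-1.50.
- On scale, the criterion is worded for the starting dose, so the dose ratio is the natural reading. The example was chosen close to a boundary.

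**The case for a change.** The strongest case for acting is that a rule able to end recruitment early should have its quantity fixed before the data cut-off, and that one sentence, or one citation of the modelling plan, would do it at almost no cost. Reusing the approach of interims 1 and 2 does not fully answer this, because the rule printed for them in Section 3.1 compares a point estimate with 30% and 50% deviations, uses no interval, and names no weight either. Section 10.4 still speaks of two interims when it refers to the modelling plan. Falling back on criterion 2 is not neutral, since it brings in a judgement on safety data.

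What stands is that neither the protocol nor the SAP defines the quantity or the reference estimate. What does not stand is that this makes the rule wrong. Neither reading is shown to be better or the stated limits unsuitable, and if the update is a common shift across weights the two readings coincide apart from scale. Writing the rule as an exposure ratio would replace the dose-scale criterion rather than clarify it. The comparison with the current curve has been carried out before, and the protocol names the document where the detail belongs. That document was not available for this review, so its silence cannot be assumed.

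**Conclusion.** No change to the plan follows. The protocol text is short of one definition: the weight or common ratio at which the interval is judged, together with the reference estimate. That is working detail which the protocol delegates to the modelling data analysis plan, to be updated for interim 3, and which the modelling analysts can settle from an approach already used twice. A request to point to the relevant section of that plan would be reasonable, but it is a query and not a correction.

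The calculations show that the reading could matter. They do not measure how much. The criterion 2 figures, 83-90% against 61%, are the more relevant comparison, and they carry the same confounding by different simulations. All the probabilities assume log-normal estimates, a true ratio of 1, 10 Cohort 3 children, standard errors back-solved from Section 10.5, and interim 3 precision like that of Table 6. They should be read as indicative only.
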